### Interim Analysis Results

A separate independent and unblinded team (“Unblinded Statistical/Programming Team”) will be established to perform the analysis and prepare the TFLs. An independent and unblinded

DMC will be established to review the data and provide a recommendation regarding the continuation of the study. The Sponsor's and CROs' study teams and the other blinded team members will remain blinded. The outputs produced for the interim analysis will include a designation as "Interim Analysis" next to the analysis population.

## 7.6 Examinations of Subgroups

The analyses on the percentage of subjects who have treatment success following a single and/or two installations of study drug will be also analyzed for each of the below subgroups:

- Age (<18, ≥18-<65, ≥65-<85, ≥85 years).
- Sex (Female, Male).
- BMI (<18.5 kg/m^2, ≥18.5-<25 kg/m^2, ≥25.0-<30 kg/m^2, ≥30.0 kg/m^2).
- Country.
- Region (US vs Non-US).
- Type of CVAD (Non-tunneled or Tunneled Central Venous Catheter (CVC), Implanted Ports, Peripherally Inserted Central Catheters (PICCs)).

Other category is excluded from the analyses.

- Number of lumens (single lumen, multi-lumen: 2, multi-lumen: 3, multi-lumen: 4).
- Where and by whom was the CVAD identified as dysfunctional (Patient/caregiver identified, Healthcare provider not at study site, Healthcare provider at study site)
- Duration of CVAD dysfunction (0-5 hours, >5-48 hours)
- Race (American Indian or Alaska Native, Asian, Black or African American, Native Hawaiian or Other Pacific Islander, White, Other, Not Reported).

In case of multiple races for a same subject, the combination of the races will be displayed as a new category.

- Ethnicity (Hispanic or Latino, Not Hispanic or Latino, Not Reported, Unknown).

For all subgroup analyses, any category with fewer than 1 subject will be excluded from the analyses.

For treatment comparisons, if one of the 2 treatment groups compared has fewer than 3 subjects, the comparison will not be performed.

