## 2 Study Design

This is a phase 3 multinational, multicenter, prospective, randomized, double-blind, parallel-group, active and placebo-controlled study examining the effect of instillations of CUSA-081 versus placebo or alteplase in subjects with dysfunctional non-hemodialysis CVADs. Restoration of CVAD function is defined as follows: the ability to both withdraw at least 3 mL of blood and infuse 5 mL of saline.

Subjects will be screened according to the Study Inclusion and Exclusion criteria and will be candidates for randomization if all eligibility criteria are met.

A minimum of 841 subjects, within approximately 100 sites, will be randomized, in a 9:1:6 ratio of CUSA-081:Placebo:alteplase in order to achieve a minimum of 800 subjects completing the study:

Treatment Arm A (CUSA-081 [reteplase])	473 subjects
Treatment Arm B (Placebo)	53 subjects
Treatment Arm C (alteplase)	315 subjects

A total of 2-3 visits will be performed during the study, as follows (refer to the Study Treatment Schema in Figure 1 for more details):

[figure not shown]
- Screening (Baseline Visit) (Day 0 or Day 1).
- Treatment Visit 1 (V1) (Day 1):
  - Subjects will receive the first instillation of study drug (CUSA-081, placebo or alteplase) into the catheter via the single lumen designated for this study.
  - If patency is not restored after 90 minutes following the first instillation, a second dose of study drug (same drug as at first instillation) will be administered.
- Follow-up Visit 2 (V2) (Day 30 ± 2 days) (can be performed by telephone).

An extra visit could be performed as Screening (Baseline Visit) for logistical reasons. Day 1 must be the following calendar day (for example, Monday and Tuesday; not Friday and Monday). Informed consent will be signed during this visit.

Safety will be monitored throughout the study.

The end of the trial is defined as the last follow-up contact of the last subject to receive study drug in the trial.

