## 5 Sample Size

For the primary assessment of the superiority of CUSA-081 vs. placebo, a sample size of 450 in the active arm (CUSA-081), and 50 in the control arm (placebo), will provide >99% power to detect a difference of  $\geq 35\%$  using a two-sided test at significance level of 0.05. The expected placebo response rate is approximately 20%.

For the assessment of the non-inferiority of CUSA-081 vs alteplase, a sample size of 450 in the active arm (CUSA-081), and 300 in the control arm (alteplase) will provide 87% power at the 2.5% significance level (that is by using one-sided 97.5% confidence intervals (CI)) with a non-inferiority margin of -10%, assuming an equal response rate of 75% in the control arm (alteplase), and the active (CUSA-081) arm. A sample size of 450 in the active arm (CUSA-081), and 300 in the control arm (alteplase) will also provide 92% power to detect a difference of 10% between the success rates using a two-sided test at significance level of 0.05.

A minimum of 841 subjects will be randomized in order to achieve a minimum of 800 subjects completing the study.

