# 7 General Considerations for Statistical Analysis

## 7.1 Statistical Significance

All tests of superiority hypotheses will be two-sided and conducted at the 0.05 significance level, and all confidence intervals will be two-sided at the 95% confidence level.

The assessment of non-inferiority will be based on the 2.5% level of significance (using one-sided 97.5% confidence intervals) with a non-inferiority margin of -10%.

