Table 14.1.11.1	Concomitant Medications (Full Analysis Set)	CMT002		Same as Table 14.1.9.1

Table Number	Table Title	Template Code	Notes	Footnotes/Source Listing Number
Table 14.1.11.2	Concomitant Medications (Safety Set)	CMT002		Same as Table 14.1.9.1
Table 14.2.1.1.1	Summary and Statistical Analysis of Proportion of Subjects with Treatment Success Up to 90 Minutes Following a Single Instillation of Study Drug (Full Analysis Set)	ANT007	
 
- Replace “Adjusted Mean” with “Proportion of Treatment Success (95% CI)” and “Adjusted Mean difference” with “Difference in Proportions (95% CI)”.
 
- Do not display Parameter column.
 
- Replace Study Day by Timepoint.
 
- Timepoints to be presented: 30, 60 and 90 mins.
 
- Add column for P-value for all the treatment comparison at all timepoints as last column.
 
- In the column Treatment and after all treatments listed, add the different comparisons: CUSA-081 vs Placebo, CUSA-081 vs Alteplase, Alteplase vs Placebo.
 
- Replace ‘n’ by ‘n Success’.
 
	
Source: Listing 16.2.6.1
 
Footnotes: [1] ‘n Success’ corresponds to the number of subjects with treatment success. [2] The 95% confidence intervals of proportions and difference of proportions are based on Wald method. [3] The p-value is based on a 2-sample Z test for proportions. [4] Percentages are based on the number of subjects in the treatment group.

Table 14.2.1.1.2 ***	SAS Output: Summary and Statistical Analysis of Proportion of Subjects with Treatment Success Up to 90 Minutes Following a Single Instillation of Study Drug (Full Analysis Set)		Raw SAS output	
Table 14.2.1.2	Summary and Sensitivity Analysis of Proportion of Subjects with Treatment Success Up to 90 Minutes Following a Single Instillation of Study Drug (Intention-to-Treat Set)	ANT007	
Same as Table 14.2.1.1.1
 
The randomized but non-treated subjects will be considered as non-responders.
	Same as Table 14.2.1.1.1
Table 14.2.1.3.1	Summary and Sensitivity Analysis of Proportion of Subjects with Treatment Success Up to 90 Minutes Following a Single Instillation of Study Drug (Per-Protocol Set)	ANT007	Same as Table 14.2.1.1.1	Same as Table 14.2.1.1.1

Table Number	Table Title	Template Code	Notes	Footnotes/Source Listing Number

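### The subgroup tables give p-values within each level of 11 factors but plan no treatment-by-subgroup test, so those p-values do not address whether the effect differs between subgroups

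*SAP*

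**What the plan says.** - SAP 7.6 lists age, sex, BMI, country, region, CVAD type, number of lumens, where and by whom the dysfunction was identified, its duration, race and ethnicity. It says that treatment success "will be also analyzed for each of the below subgroups".
- The only limit on a comparison is size: "if one of the 2 treatment groups compared has fewer than 3 subjects, the comparison will not be performed".
- SAP 16.1 has 11 subgroup tables for the first instillation (14.2.1.4.1 to 14.2.1.4.11) and 11 for up to two instillations (14.2.2.4.1 to 14.2.2.4.11). All inherit the layout of Table 14.2.1.1.1, whose note reads "Add column for P-value for all the treatment comparison at all timepoints as last column". That layout has three comparisons: CUSA-081 against placebo, CUSA-081 against alteplase, and alteplase against placebo. The time points are 30, 60 and 90 minutes in the first set and 120, 150 and 180 minutes in the second.
- The same shells give the difference in proportions with a Wald 95% confidence interval for each level.
- SAP 7.2.1 restricts the closed testing procedure to the primary objective and secondary objectives 1 to 4, and makes no multiplicity adjustment elsewhere.
- No interaction or heterogeneity test appears in SAP 7.6, section 9, the SAS code in section 14 or the table list. The logistic model in SAP 14.4 has main effects of treatment, age category and region only.

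**The concern.** A subgroup section is there to ask whether the treatment effect varies across kinds of patient or catheter. A p-value computed inside one level answers another question: whether the two arms differ in that level. One level can be significant and another not simply because the first is larger. The plan therefore produces several hundred tests and leaves out the one that bears on its question.

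Two misreadings follow. For CUSA-081 against alteplase, where the non-inferiority calculation assumes equal rates, a scatter of small p-values is expected by chance and could be reported as a subgroup in which one drug is better. For comparisons with placebo, 53 planned subjects are split across as many as seven levels, so a large true effect can look absent in a small cell.

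**Working it through.** **Inputs from the documents.** Superiority tests: "All tests of superiority hypotheses will be two-sided and conducted at the 0.05 significance level" (SAP 7.1). Non-inferiority: "The assessment of non-inferiority will be based on the 2.5% level of significance", margin -10 points (SAP 7.1). Arm sizes for power: 450 and 300 (SAP 5). Success rate: "assuming an equal response rate of 75% in the control arm (alteplase), and the active (CUSA-081) arm" (SAP 5). Allocation: "in a 9:1:6 ratio of CUSA-081:Placebo:alteplase" (SAP 2).

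**Reproducing the plan's own figures.** The plan states no error rate for subgroups, so its power figures serve as the check.
- Non-inferiority: SE = sqrt(0.75×0.25/450 + 0.75×0.25/300) = 0.0323. Power = Φ(0.10/0.0323 − 1.96) = Φ(1.14) = 87.3%, against 87% stated.
- Superiority: "A sample size of 450 in the active arm (CUSA-081), and 300 in the control arm (alteplase) will also provide 92% power" for a 10-point difference. Taking 75% against 85% gives 92.2%, which agrees.

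**Counting the p-values.** Without country, and without the under-18 level (the protocol admits adults only), the levels in the order of SAP 7.6 are 3 + 2 + 4 + 2 + 3 + 4 + 3 + 2 + 7 + 4 = 34.
- All comparisons: 34 × 3 × 6 = 612.
- CUSA-081 against alteplase: 34 × 6 = 204.
- The two comparisons with placebo: 612 − 204 = 408.

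These are ceilings before the rule on fewer than 3 subjects. Country adds levels: with an assumed 2 to 8 countries the total is 648 to 756.

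**Chance findings, CUSA-081 against alteplase, no true difference.**
- Expected number below 0.05: 204 × 0.05 = 10.2.
- At 90 minutes, if the 34 tests were independent: 1 − 0.95^34 = 82.5%. Subgroups overlap, so this is too high.

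A simulation of 3,000 trials per sample size allowed for overlap, for success carried forward over the six time points, and for the rule on fewer than 3 subjects. The documents do not give its inputs, so these are assumptions: five countries (70/10/10/6/4%), with region taken as the first against the rest; age 55/42/3; sex 50/50; BMI 6/32/32/30; CVAD type 20/40/40; lumens 55/38/6/1; identified by 10/20/70; duration 60/40; race 1/3/14/0.5/76/3.5/2; ethnicity 12/83/3/2; success 50/65/75/80/83/85% at 30 to 180 minutes. SAP 12 says the study stopped early without giving the final number, so a range is shown.

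| Total N (three arms) | Levels tested (mean) | At least one p<0.05 at 90 min | Expected count at 90 min | At least one p<0.05, six time points | Expected count, six time points |
|---|---|---|---|---|---|
| 841 | 37.0 | 72% | 1.8 | 98% | 11.0 |
| 416 | 34.5 | 69% | 1.7 | 97% | 9.9 |
| 200 | 30.2 | 62% | 1.4 | 94% | 8.5 |

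In trials where the overall 90-minute test is not significant the results are nearly the same: 71%, 67% and 60% at 90 minutes.

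**Smallest permitted cell.** With 3/3 against 0/3, the chi-square statistic (the square of z, SAP 14.1) is 6, p = 0.014. Fisher's exact test gives 2/20 = 0.10, and the Wald interval has zero width.

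**What an interaction test would offer.** For a two-level factor split evenly, with 450 against 300, the SE of the difference between the two effects is 2 × 0.0323 = 0.0646. Power at two-sided 0.05 is Φ(gap/0.0646 − 1.96):
- 10 points: 34%
- 15 points: 64%
- 20 points: 87%

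With 11 such tests and no true heterogeneity, the chance of at least one below 0.05 is 1 − 0.95^11 = 43% if independent. The simulation gave 45% to 50% with an approximate heterogeneity statistic that left out levels with fewer than 10 per arm.

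**The case against.** The strongest reply is that little depends on these tables. Subgroups sit openly outside the closed testing procedure, and protocol 12.3.5 and SAP 9.3.1 speak of covariate and subgroup analyses as things that may be explored. That stands: no confirmatory claim or error rate is affected. It does not settle the point, because SAP 7.6 neither labels the p-values exploratory nor says how to read them.

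It is also fair that the shells already give a difference and confidence interval per level, so effects can be compared by eye. What is missing is a formal comparison across levels.

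A reader might infer more than the documents support:
- That all 612 p-values are chances for a false positive. Two thirds compare an active drug with placebo. SAP 5 plans for a CUSA-081 effect of at least 35 points, and SAP 5.1 puts alteplase at least 37.6 points above placebo, so significance there would not be a chance finding.
- That a chance finding is near certain. Under the assumptions above that is so only over all six time points (94% to 98%), which are nested looks at the same subjects. At the primary time point it is likely, not near certain.
- That every cell is tested. The rule on fewer than 3 subjects blanks some, and the under-18 level is empty.

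Finally, interaction tests have weaknesses of their own, low power and unadjusted multiplicity. That stands and should be stated with the fix.

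**Conclusion.** The point holds as a modest, inexpensive improvement. The subgroup tables report p-values that do not address differences between subgroups, and no planned analysis does so formally. The level count of 34 and the ceiling of 204 follow directly from the SAP. The figures of about 8 to 11 chance results and of 62% to 72% at 90 minutes apply to CUSA-081 against alteplase with no true difference; they rest on the assumed prevalences, five countries, success rates over time and total N between 200 and 841. For comparisons with placebo the concern is false reassurance about lack of effect in small cells, not false positives. The trial's confirmatory conclusions are not in question.

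**What to change.** In SAP 7.6 and the 22 subgroup shells:
1. Drop the within-level p-values and keep the difference with its 95% confidence interval in each level.
2. Add one treatment-by-subgroup interaction p-value per factor at 90 minutes for CUSA-081 against alteplase, and against placebo where cell sizes allow. Name the scale; the difference in proportions would match the main analysis.
3. Label these p-values exploratory and unadjusted. State that power is low (about 34% for a 10-point difference in effect under the even-split case above, and less after early stopping) and that 11 independent tests carry about a 43% chance of at least one false interaction.

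The cost is SAP wording, shell edits and a short piece of code. No new data are needed and the output shrinks. If the SAP can no longer be amended, SAP 1 already provides for explaining deviations in the clinical study report. A forest plot or a larger minimum cell size is a matter of preference and not part of this point.

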12.3.5 Secondary Efficacy Variables

The number and percent of subjects with treatment success by treatment and time point will be summarized. The rate difference and associated 95% Wald confidence intervals between CUSA-081 vs. placebo and alteplase will be estimated. The between treatment comparisons will be performed using a 2-sample z test.

The rate of recurrent catheter dysfunction defined as first re-occlusion within 30 days following treatment will be analyzed using the Kaplan-Meier method and summarized with median, 25th and 75th percentiles, and 95% confidence intervals. The rate of recurrent catheter dysfunction will be estimated. This analysis will be based on all subjects with treatment success following up to two administrations of study drug with a total dwell time up to 180 minutes.

Additional efficacy analyses including demographics and baseline characteristics as covariate/subgroup may be explored.

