## 14 SAS Code

### 14.1 Comparison of Two Proportions Using 2-Sample Z Test

```
PROC FREQ DATA = <dataset>;  
    TABLES trt01pn*Response / RISKDIFF (CL=(WALD) COLUMN=2);  
    WHERE <population> = "Y" and ATPT = <timepoint>;  
RUN;
```

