#### Notes:

- TRT01PN represents the treatment arm, incorporating the following ordering: 1=CUSA-081, 2=Placebo and 3=Alteplase;
- Response represents the treatment success indicator (1=Yes, 0=No).
- The Chi-square statistic corresponds to the square of the Z-statistics (so the p-value for Table 14.2.1.1.1 corresponds to the Chi-square p-value).

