Table 14.2.1.3.2 ***	SAS Output: Summary and Sensitivity Analysis of Proportion of Subjects with Treatment Success Up to 90 Minutes Following a Single Instillation of Study Drug (Per-Protocol Set)		Raw SAS output	
Table 14.2.1.4.1	Summary and Statistical Analysis of Proportion of Subjects with Treatment Success Up to 90 Minutes Following a Single Instillation of Study Drug by Age (Full Analysis Set)	ANT007	
Same as Table 14.2.1.1.1
 
 
- Add a subgroup title for each age category.
 
- N should display the number of subjects within the subgroup category.
 
- Categories with fewer than 1 randomized patients are excluded from this analysis.
 
- For the treatment comparison rows, if there are <3 subjects in one of the 2 arms compared, then the columns “Difference in Proportions (95% CI)” and “P-Value” will be left empty.
 
- Footnotes [5] and [6] to be displayed only if applicable to the output (it will be displayed on all pages even if not applicable to a specific subgroup).
 
	
Source: Listing 16.2.6.1
 
Footnotes: [1] ‘n Success’ corresponds to the number of subjects with treatment success. [2] The 95% confidence intervals of proportions and difference of proportions are based on Wald method. [3] The p-value is based on a 2-sample Z test for proportions. [4] Percentages are based on the number of subjects in the treatment group and in the subgroup. [5] Comparisons with less than 3 subjects in one of the treatment group will not be performed. [6] NE = Not estimable.

Table 14.2.1.4.2	Summary and Statistical Analysis of Proportion of Subjects with Treatment Success Up to 90 Minutes Following a Single Instillation of Study Drug by Sex (Full Analysis Set)	ANT007	Same as Table 14.2.1.4.1	Same as Table 14.2.1.4.1

Table Number	Table Title	Template Code	Notes	Footnotes/Source Listing Number
Table 14.2.1.4.3	Summary and Statistical Analysis of Proportion of Subjects with Treatment Success Up to 90 Minutes Following a Single Instillation of Study Drug by Race (Full Analysis Set)	ANT007	Same as Table 14.2.1.4.1	Same as Table 14.2.1.4.1
Table 14.2.1.4.4	Summary and Statistical Analysis of Proportion of Subjects with Treatment Success Up to 90 Minutes Following a Single Instillation of Study Drug by Ethnicity (Full Analysis Set)	ANT007	Same as Table 14.2.1.4.1	Same as Table 14.2.1.4.1

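### The subgroup tables print Wald 95% intervals down to 3 subjects per arm; against a 3-subject placebo cell they cover about 65% and can contradict the p-value in the same row

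*SAP*

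**What the plan says.** SAP 7.6 lists 11 subgroup variables and sets two size limits. On categories it says that "any category with fewer than 1 subject will be excluded from the analyses". On contrasts it says: "For treatment comparisons, if one of the 2 treatment groups compared has fewer than 3 subjects, the comparison will not be performed". There is no minimum per arm for showing a single rate.

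The results fill 22 tables in SAP 16.1: 14.2.1.4.1 to 14.2.1.4.11 (up to 90 minutes) and 14.2.2.4.1 to 14.2.2.4.11 (up to 180 minutes). Footnote 2 reads "The 95% confidence intervals of proportions and difference of proportions are based on Wald method", and footnote 3 reads "The p-value is based on a 2-sample Z test for proportions". The code in SAP 14.1 requests "RISKDIFF (CL=(WALD) COLUMN=2"), and its notes add that "The Chi-square statistic corresponds to the square of the Z-statistics".

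Protocol 12.3.5 also names the Wald method for the secondary comparisons: "The rate difference and associated 95% Wald confidence intervals between CUSA-081 vs. placebo and alteplase will be estimated". Neither document gives a small-sample alternative for these tables. A footnote for non-estimable results exists, but no rule says when it applies.

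**The concern.** Two features combine badly in small cells.

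- The Wald interval estimates each arm's variance as p(1 − p)/n. An arm with no successes, or only successes, contributes zero. The single-rate interval then collapses to a point, and the interval for the difference reflects the other arm alone.
- The p-value in the same row uses the pooled variance, which does not collapse. Interval and p-value can therefore disagree.

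The 9:1:6 allocation makes this a placebo problem. Of 53 planned placebo subjects, a category holding 3/53 = 5.7%, 5/53 = 9.4% or 10/53 = 18.9% of the trial has an expected 3, 5 or 10 on placebo. SAP 7.6 splits by country, race, number of lumens, BMI band and age including 85 and over, so such categories are plausible. SAP Section 12 records that the trial stopped early, so the cells shrink further if fewer than 841 subjects were randomized.

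The risk is that a reader takes an interval excluding zero as a subgroup effect when the test beside it shows nothing.

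**Working it through.** **Inputs.** Placebo rate 20% and CUSA-081 rate 75% (SAP Section 5); 55% is the same section's 20% plus its 35-point difference. Allocation is 9:1 for CUSA-081 vs placebo, giving illustrative cells of 27/3, 45/5 and 90/10. Intervals are 95% and tests are two-sided at 0.05 (SAP 7.1).

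**The plan's own figures.** The documents give no coverage figure, but their power statements reproduce, which confirms that the rates are read correctly:

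- Superiority to placebo, 450/50, 55% vs 20%: 99.96% (stated as above 99%).
- Non-inferiority, 450/300, 75% each: 0.10/√[0.1875(1/450 + 1/300)] − 1.96 = 3.098 − 1.960 = 1.138, so power is 87.3% (stated 87%).
- Superiority to alteplase, 85% vs 75%: 92.2% (stated 92%).

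**One cell by hand: 5/27 vs 0/3.** The difference is 0.1852.

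- Wald: SE = √[0.1852 × 0.8148/27 + 0] = 0.0748; 0.1852 ± 1.96 × 0.0748 gives 3.9% to 33.2%.
- Pooled test: p̄ = 5/30 = 0.1667; SE = √[0.1667 × 0.8333 × (1/27 + 1/3)] = 0.2268; z = 0.8165, p = 0.41.
- Miettinen-Nurminen (MN): −40.3% to 37.0%.

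In the other direction, 23/27 vs 1/3 gives a Wald interval of −3.1% to 106.9%, with an impossible upper limit, beside p = 0.033.

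**Single rates, true rate 20%.** At n = 3, P(0/3) = 0.8³ = 0.512 and P(3/3) = 0.008, so 52% of cells have a zero-width interval. Wald covers only at 1/3 or 2/3: 0.384 + 0.096 = 48.0%. Wilson covers 89.6% and Clopper-Pearson 99.2%. At n = 1 the Wald interval always has zero width.

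**Differences.** Every binomial outcome was enumerated and the coverage of the true difference summed, at 75% vs 20%:

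| Cell | Wald | Newcombe | MN |
|---|---|---|---|
| 27/3 | 65.2% | 94.9% | 95.5% |
| 45/5 | 69.8% | 95.4% | 96.6% |
| 90/10 | 87.7% | 95.7% | 96.2% |

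At 27/3, Wald covers 69.0% at 55% vs 20%, and 55.6% with no effect (20% in both arms).

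**Disagreement with the p-value at 27/3.** This counts an interval that excludes zero with p ≥ 0.05, or the reverse:

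| True rates | Wald | Newcombe | MN |
|---|---|---|---|
| 20% vs 20% | 43.6% | 0.01% | 0.0% |
| 55% vs 20% | 38.5% | 7.2% | 0.0% |
| 75% vs 20% | 7.0% | 1.6% | 0.0% |

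With no effect, 41.9 of the 43.6 points are intervals favouring CUSA-081 without a significant test. Under no effect, Wald disagreement is still 34.6% at 45/5 and 12.5% at 90/10. MN agrees with the test because, at a zero difference, its variance is the pooled variance times N/(N − 1). MN disagreement is 0 at 45/5 and at most 0.7% at 90/10.

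**Where the problem stops.** CUSA-081 vs alteplase at 27/18 and 75% each: Wald covers 93.9%, with 1.5% disagreement. Overall placebo contrast at 473/53, 75% vs 20%: Wald covers 93.6% and Newcombe 95.1%, with mean widths of 0.226 and 0.224. The size of the z-test at a common rate of 20% is 4.9% at 473/53 and 4.2% at 27/3.

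**The case against.** The best defence is that these tables are exploratory. SAP 7.2.1 leaves them outside the closed testing procedure, each table shows the number of subjects per category, and the p-value beside the interval keeps its size (4.2% at 27/3). That stands, and it limits the consequence to what is displayed. It does not justify labelling an interval 95% when it covers 65%.

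The 27/3 cell is also the smallest placebo contrast the rule would allow at the 9:1 ratio, and real cell sizes are unknown. This stands as a caveat. Coverage is still below 90% at 90/10, however, so the problem is not confined to the threshold.

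The largest disagreement figure assumes no effect, which is far from the plan's expectation. At 75% vs 20% it is 7.0%, of which only 3.45 points are intervals excluding zero without a significant test. But at 55% vs 20%, the plan's own superiority assumption, it is 38.5%.

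It is fair to say that alteplase contrasts are nearly unaffected. It is also fair that Newcombe, although it restores coverage, still disagrees with the test in 7.2% of 27/3 cells at 55% vs 20%. That favours MN. Finally, changing the overall placebo contrasts as well would put two interval methods in one table for a small gain, so that step is optional.

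**Conclusion.** The concern holds. Followed as written, the SAP would print 95% intervals for placebo contrasts in small subgroups with actual coverage of about 65% to 88% (3 to 10 placebo subjects, 75% vs 20%). Some rows would show an interval that contradicts their own p-value. Single placebo rates would often have zero-width intervals.

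The figures rest on the plan's assumed rates and on illustrative cells built from the 9:1 ratio. The documents give neither a subgroup distribution nor a final sample size. The damage is confined to displayed subgroup intervals, mainly those involving placebo. Superiority is decided by the z-test, the overall non-inferiority limit is sound, and no confirmatory conclusion changes. The point should be corrected, but it does not threaten the trial's main result.

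**What to change.** - In the 22 subgroup tables, replace the Wald interval for differences with Miettinen-Nurminen (RISKDIFF CL=(MN)). Newcombe is acceptable for coverage but agrees less well with the p-value in the smallest cells.
- Use Wilson or Clopper-Pearson intervals for single rates. Clopper-Pearson is the more cautious choice at n = 3. The SAP already uses exact binomial intervals for adverse events of special interest (10.2.1).
- Update footnote 2 in both table families.
- Keep the z-test p-value throughout and the Wald limit for the overall non-inferiority test. Using MN for the overall placebo contrasts is optional.
- Record the departure from the Wald method in SAP Section 12 before unblinding.

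The programming cost is small: the subgroup call must be separated from the shared code in SAP 14.1, with one option changed and a separate request for single-rate intervals. Intervals widen noticeably only in the smallest cells. At 75% vs 20%, mean width at 27/3 is 0.700 for Wald, 0.753 for Newcombe and 0.777 for MN; at 90/10 it is 0.485, 0.476 and 0.485.
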